### **Recruitment**

Subjects will be recruited from the outpatient clinics at the Washington DC VAMC. The DC VAMC annually has over 100 admissions for stroke. [name], has WOC status at the DC VAMC and will confirm that patients meet study criteria. Additionally, veterans will be recruited from nearby MedStar National Rehabilitation Hospital (NRH), Washington Hospital Center (WHC), and Medstar Health outpatient clinics.

The inclusion criteria are: 1) Age 21 or older; 2) ischemic or hemorrhagic stroke (with confirmatory neuroimaging) that occurred more than 6 months before entering the study; 3) presence of voluntary hand activity indicated by a score of at least 1 on the finger mass extension/grasp release item of the Fugl-Meyer Test of Motor Function; 4) adequate cognitive status, as determined by Mini-Mental Status Examination (Bleeker 1988) score >24; 5) no upper extremity injury or conditions that limited use prior to the stroke. Subjects will be excluded if they: 1) cannot give informed consent; 2) have clinically significant fluctuations in mental status within a month of enrollment; 3) were not independent prior to the stroke as measured by scores <95 on the Barthel Index (de Morton 2008) or >1 on the Modified Rankin Scale (Quinn 2009); 4) have hemispatial neglect as determined by >3 errors on the Star Cancellation Test (Manly 2009); 5) have severe sensory loss as determined by a score of 2 on the sensory item of the NIHSS (Lai 1988); 6) receiving oral or injected antispasticity medications during study treatment; 7) pain that interferes with daily activities; 8) history of prior stroke.

In a previous study in chronic stroke, we found that the dropout rate was 16.7%, so we will plan to **recruit 46 subjects**. Subjects who drop out of the study will be replaced until a total of **38 subjects complete the protocols**. All therapy will be in addition to the regular PT and OT subjects may be receiving as part of their outpatient treatment. The amount of outside PT or OT targeting arm or hand function received by subjects while enrolled in the study will be logged and used as a potential covariate in the analysis.

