## **5. Study Design**

### **Overview**

The robotic system will be used in a clinical trial with chronic stroke subjects with impaired upper extremity function. 46 subjects will be randomly assigned to an experimental or control group. The experimental group will receive 1-hour robotic training sessions, 3 times per week for a total of 12 sessions supervised by a research assistant. Immediately following this robot training, these subjects will receive the same dosage and schedule (1-hour sessions, 3 times/week, 12 total sessions) of conventional one-on-one therapy from an occupational therapist. The control group will receive 24 hours of conventional one-on-one therapy on the same schedule (1-hour sessions, 3 times/week). Clinical and biomechanical evaluations will be performed before treatment, after 12 hours of treatment, after 24 hours of treatment and at a 6-month follow-up.

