### Data analysis

Prior to conducting the main analyses, summary statistics, histograms, and scatter plots will be inspected to verify that distribution assumptions are met. Adjustments (e.g., transformations) to the main dependent measures will be made as necessary to address any problems (e.g., skewness, outliers) that these preliminary analyses uncover. To test Hypotheses, a series of mixed model ANOVAs will be tested, one for each dependent variable, with the within-subject variable being timepoint (pre, after 12 hours of treatment, after 24 hours of treatment, 6 month followup) and the between-subject variable of group (experimental vs. control). A significant effect of timepoint or a significant timepoint x group interaction would be followed with a series of paired t-tests, with Bonferoni corrections. Hypothesis I will be tested with a paired t-test between the pre and post-robotic timepoint (after 12 hours of robotic treatment). Hypothesis II will be tested with a paired t-test between the pre and post-treatment timepoint in the experimental group (after 12 hours of robot and 12 hours of conventional therapy). Additionally a z-test will be performed for the hypothesis that the proportion of subjects with 10% or greater gain at the post-treatment timepoint is significantly greater than zero. A final paired t-test and z-test between pre and 6-month followup timepoints will be performed. If a change is statistically significant, mean changes will be compared to predetermined MCID values of 10% of full scale. To test Hypothesis III, the timepoint x group interaction effect will be examined in the mixed model ANOVA. If significant, gains in the dependent variables will be calculated at the post-treatment and 6-month timepoints (relative to the pre timepoint), and between-group differences will be tested with unpaired t-tests, with Bonferoni corrections.

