To address Hypothesis III, we calculated the power to detect the expected differences in gains between the experimental and control groups. The experimental treatment in our pilot study produced gains of 7 (sd=4.9) in the Fugl-Meyer. A recent study reported gains of 2.47 (sd=1.67) on the Fugl-Meyer after 24 hours of conventional therapy in 35 stroke subjects with similar intake Fugl-Meyer scores as in our pilot study (FM = 22.4 vs. 21) (Klamroth-Marganska 2014). Using these data, the mean difference in treatments will have an effect size of 1.9. For a 1-tailed unpaired t-test, **N=5** subjects in each treatment group are needed to detect this difference with power > 0.80. Similarly for the ARAT, we had gains of 5.6 (sd=4.7) after the experimental treatment in our pilot study. A different study (Fleming 2015) reported gains of 1.0 (sd=5.7) after 24 hours of conventional therapy in 17 chronic stroke subjects with similar intake ARAT scores as in our pilot study (ARAT = 26.6 vs. 20.9). Using these data, the mean difference in treatments will have an effect size of 0.84. For a 1-tailed unpaired t-test, **N=19** subjects in each treatment group will detect this difference with power > 0.80.

Therefore with **N=19** subjects in each treatment group, we will detect the anticipated pre-post changes and group differences in the ARAT and Fugl-Meyer. We had a dropout rate of 0.167 in the pilot study. Therefore, we will plan for this and recruit 23 subjects into each treatment group. We have no pilot data on the MAL to perform a power analysis for the outcome.

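### Dropout is provided for twice, by inflating to 46 and by replacing until 38 complete; enrolment is left uncapped and the analysis defaults in practice to completers

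*Combined protocol and SAP*

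**What the plan says.** Section 5, Recruitment, takes its dropout rate from earlier experience ("In a previous study in chronic stroke, we found that the dropout rate was 16.7" per cent) and concludes that the trial should "recruit 46 subjects". The next sentence reads "Subjects who drop out of the study will be replaced until a total of" "38 subjects complete the protocols".

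Elsewhere 46 is a fixed number. The specific aim gives N=46, the Overview says "46 subjects will be randomly assigned to an experimental or control group", and the Power Analysis, having arrived at 19 per arm, says "Therefore, we will plan for this and recruit 23 subjects into each treatment group".

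The Data analysis section names mixed model ANOVAs "with the within-subject variable being timepoint (pre, after 12 hours of treatment, after 24 hours of treatment, 6 month followup") and group as the between-subject factor. Hypotheses I and II are then decided by paired t-tests from the pre-treatment score. Hypothesis III is decided, if the interaction is significant, by unpaired t-tests on gains from the pre-treatment score.

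The sections available for review do not state:
- whether 38 means 19 per arm;
- whether completing means the end of treatment or the 6-month visit;
- whether a replacement is newly randomised or takes the dropout's arm;
- any upper limit on enrolment;
- an analysis set, a missing-data method, or follow-up of subjects who drop out.

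**The concern.** Inflating the sample and replacing dropouts are two ways of dealing with the same loss. Inflation fixes the number randomised and lets the number of completers vary. Replacement fixes the number of completers and lets the number randomised vary. The plan states both, so the size of the trial depends on how many subjects leave.

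The larger issue is who is compared. A rule that counts completers, joined to tests that need a baseline and a later score, has no natural place for a randomised subject who leaves. The two arms look different to subjects: for the first 12 hours one has robot sessions run by a research assistant and the other has one-on-one therapy. Subjects must also stay to a 6-month visit. Dropout that depends on both arm and progress is plausible. If it occurs, the group difference can be biased in either direction. Hypotheses I and II are within-arm gains with no control contrast, so losing poor responders raises them even when dropout is equal in the two arms.

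**Working it through.** **1. The plan's own figures.** The inputs, from Power Analysis, are ARAT gains of 5.6 (SD 4.7) and 1.0 (SD 5.7, n=17), d=0.84, a one-tailed unpaired t-test and power above 0.80. Alpha is stated as 0.05 for Hypotheses I and II and is assumed the same for III. The pilot arm size is assumed to be 6.
- Pooled SD = √[(5×4.7² + 16×5.7²)/21] = 5.48, and 4.6/5.48 = 0.84. This reproduces.
- Noncentral-t power at d=0.84 and 19 per arm is 0.815. This reproduces.
- 19/0.833 = 22.8, giving 23 per arm; 38/0.833 = 45.6, giving 46. This reproduces.

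So 46 already carries the whole dropout allowance.

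**2. Number randomised under replacement.** If each subject drops out independently with probability p, the number needed for 38 completers is negative binomial with mean 38/(1−p). More than 46 are needed when the first 46 contain fewer than 38 completers. If 19 per arm are required, the chance that at least one arm needs more than 23 is 1 − (1 − P_arm)². At 16.7% dropout P_arm = 0.337, which gives 1 − 0.663² = 0.56.

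| Dropout | Mean needed | 5th–95th percentile | P(more than 46) | P(either arm needs more than 23) |
|---|---|---|---|---|
| 10% | 42.2 | 39–46 | 0.04 | 0.14 |
| 16.7% | 45.6 | 41–51 | 0.36 | 0.56 |
| 25% | 50.7 | 44–58 | 0.85 | 0.92 |
| 30% | 54.3 | 47–63 | 0.96 | 0.98 |

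The spread of rates is reasonable. The Background gives 12 pilot subjects; if 0.167 is 2 of 12 (an assumption), its exact 95% interval is 2% to 48%.

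**3. Between-arm bias under no true effect.** Suppose subjects with the worst expected gain tend to leave, with correlation ρ between dropout tendency and gain (assumed 0.3 to 0.5). In SD units the bias is ρ[h(q_E) − h(q_C)], where h(q) = φ(z_q)/(1−q) and q is the dropout proportion in each arm. The SD is √[(4.7²+5.7²)/2] = 5.22. Type I error is one-sided, with 19 analysed per arm.
- Equal 16.7% dropout, same mechanism: bias 0, type I error 0.05.
- 6 v 2 of 23: the bracket is 0.266; bias 0.08 to 0.13 SD, or 0.4 to 0.7 ARAT points; type I error 0.08 to 0.11.
- 8 v 0 of 23: the bracket is 0.567; bias 0.17 to 0.28 SD, or 0.9 to 1.5 points; type I error 0.13 to 0.22.

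**4. Within-arm gains.** Take 23 in the experimental arm, 19 completers with the pilot Fugl-Meyer mean gain of 7, and 4 dropouts with mean gain g (assumed). The mean over all 23 is (19×7 + 4g)/23.
- g = 0: 133/23 = 5.78.
- g = 3.5: 147/23 = 6.39.
- g = 4.7: 151.8/23 = 6.60.

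The plan compares mean gains with 10% of full scale, which is 6.6 points. Completers alone would pass at 7. All subjects as randomised would fall short whenever dropouts averaged less than 4.7 points. This does not need unequal dropout between arms.

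**5. Effect of analysing everyone.** With 23 per arm, all outcomes obtained and d=0.84, one-sided power is 0.877. If 16.7% drop out of each arm and gain nothing (an assumption, SD unchanged), the ARAT difference is 4.6×0.833 = 3.83 and d = 0.84×0.833 = 0.70. Power at 23 per arm is then 0.755 one-sided (0.641 two-sided), and 0.80 one-sided needs 26 per arm, 52 in all. Like the plan's own figures, these ignore the Bonferroni corrections and the interaction gate.

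**The case against.** The replacement sentence is a recruitment rule. It says when enrolment ends, not who is analysed, and a trial can recruit until 38 complete and still analyse everyone randomised. A reader might infer that the rule in itself turns the trial into a completers comparison. The documents do not support that, because no section says that dropouts' data are excluded. A mixed model fitted by likelihood could use their partial data, and the mixed model ANOVAs could be implemented that way. This stands as far as the model goes. It does not rescue the t-tests that decide the hypotheses, since a subject with no later score cannot enter a test on gains.

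It can also be said that 46 and 38 form one plan, with the extra eight subjects serving as the replacements. That is fair as an expectation, since 45.6 is the mean number needed. It leaves open what happens when 46 are not enough, and the per-arm balance.

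A reader might go further and infer that 16.7% dropout undoes the randomisation. A rate alone does not. The modelled between-arm bias under no true effect is zero when rate and mechanism are the same in both arms. Large overstatements can be produced by placing zero-gain dropouts in one arm only, but nothing in the documents supports that pattern.

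Nor does the exclusion for "receiving oral or injected antispasticity medications during study treatment" help the argument. Its wording reaches past enrolment, but it stands among the eligibility criteria and no section uses it to remove a randomised subject.

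**Conclusion.** The point holds in this form. The replacement rule conflicts with the fixed 46, leaves enrolment uncapped and does not secure 19 per arm. The chance of exceeding 46 is about 36% at the planned dropout and 85% at 25%, assuming independent dropouts. Joined to tests on gains, with no stated follow-up of dropouts and no as-randomised analysis set, it leads in practice to a completers analysis. The protection given by randomisation is put at risk, not lost. Between-arm bias requires dropout that is related to outcome and differs between arms in rate or mechanism; under the assumed correlations and uneven splits it runs from 0.4 to 1.5 ARAT points. The within-arm gains of Hypotheses I and II can be inflated without any such difference. The bias figures rest on assumptions about dropouts' gains that the documents neither give nor rule out.

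**What to change.** In Recruitment, delete the replacement rule and randomise a fixed 46, 23 per group, in agreement with the Aims, Overview and Power Analysis. State that every randomised subject who consents will still be invited to the planned 12-hour, 24-hour and 6-month evaluations after stopping treatment.

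In Data analysis, make the primary analysis a likelihood-based repeated-measures model on all randomised subjects as assigned, using all available visits. Take the post-treatment and 6-month group contrasts from that model instead of from separate t-tests on gains. Report completers as secondary, with a sensitivity analysis that gives dropouts pessimistic gains. The latter is needed because the model assumes missingness at random and cannot recover the outcomes of subjects who leave with no score after baseline. Some who leave the study will decline further visits.

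The work is wording plus contact for visits already scheduled. Two downsides should be stated: completers may fall below 38, and if dropouts gain nothing the ARAT effect falls from d=0.84 to about 0.70, with one-sided power about 0.76 at 23 per arm. If the sponsor wants 0.80 under that assumption, the fixed number would be 52. Outcomes that were never recorded cannot be recovered later, so this belongs in the plan before subjects start to leave.

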### **Experimental group treatments**

Subjects will come to the clinic 3 times/week for 1-hour sessions until 12 hours of robotic treatment are received. All robot therapy sessions will be run by a research assistant trained in use of the robot. The treatment Occupational Therapist ([name]) will be available during robot training should an issue arise requiring his guidance. The training will be similar to that used in our pilot study. Tasks will include a Shelf Task, where subjects grasp objects and place them on a shelf using simultaneous shoulder elevation and elbow extension. In a Pouring Task, subjects grasp and pour from a pitcher using shoulder internal/external rotation and

simultaneous wrist pronation/supination. In Sorting, subjects grasp and move objects from one location to another using shoulder elevation and simultaneous shoulder horizontal abduction. An automatic algorithm grades the level of arm gravity compensation and assistance torques at the joints. Subjects practice first with virtual objects and then physical objects are added to increase difficulty.

Following the robotic training, subjects will undergo one-on-one therapy sessions from a Occupational Therapist with 14+ years of experience ([name]). Subjects will come to the clinic 3 times/week for 1-hour sessions until 12 hours of treatment are received. Individualized programs focusing on arm function are established at the initial training session based on assessment and patient goals. Treatment will focus on practice of specific tasks, such as reach, grasp, transport and release of various objects between different targets. Progression is done by varying the shape, size and weight of objects, altering the end range of the target or increasing the speed of movement. In weak muscles, manual therapy techniques are used to obtain isometric contractions in the shortened range. Subjects receive mobilization to restricted joints as needed and stretching exercises to increase range-of-motion. Higher functioning subjects select from isolated hand movements (typing, 'playing the piano', molding putty) and whole body activities such as swinging a tennis racquet or carrying a tray on an open hand.

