#### Control group treatments

Subjects will receive 24 hours of one-on-one treatment from the same therapist ([name]) that performed the conventional therapy for the experimental group. The treatment sessions will be identical to the conventional therapy provided to the experimental group. The treatment schedule will parallel that given to the experimental group (1-hour sessions, 3 times/week).

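### Post-treatment evaluations are tied to 12 and 24 hours received, with no provision for testing subjects who stop short, so Hypothesis III is compared only in those who finish the course

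*Combined protocol and SAP*

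**What the plan says.** **Evaluations.** The Overview in Section 5 states: "Clinical and biomechanical evaluations will be performed before treatment, after 12 hours of treatment, after 24 hours of treatment and at a 6-month follow-up". The Clinical evaluations subsection repeats these four occasions. The Data analysis subsection carries them into the model, "with the within-subject variable being timepoint (pre, after 12 hours of treatment, after 24 hours of treatment, 6 month followup", so the time factor is defined by hours received and elapsed time does not enter.

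**Treatment blocks.** Under Experimental group treatments, the robot block is described as "Subjects will come to the clinic 3 times/week for 1-hour sessions until 12 hours of robotic treatment are received", and the conventional block that follows as "Subjects will come to the clinic 3 times/week for 1-hour sessions until 12 hours of treatment are received".

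**Schedule.** The Overview fixes the planned rate: "The experimental group will receive 1-hour robotic training sessions, 3 times per week for a total of 12 sessions", and then "Immediately following this robot training, these subjects will receive the same dosage and schedule". For controls, "The treatment schedule will parallel that given to the experimental group (1-hour sessions, 3 times/week".

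**Subjects who leave.** Under Recruitment, "Subjects who drop out of the study will be replaced until a total of" 38 have completed.

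The sections available contain no statement that a subject who stops before 12 or 24 hours is still evaluated. They also give no visit window, no maximum block length and no starting point for the 6 months. Protocol Sections 7 and 8 were not available and could not be checked.

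**The concern.** Hypothesis III is the only between-group hypothesis. It compares gains at the end of treatment and at 6 months, so it needs a score at those occasions from the subjects who were randomised. If the score is due only once 24 hours have been received, someone who stops at 20 hours has no post-treatment evaluation under the plan, even if willing to attend one.

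Finishing 24 sessions is an event after randomisation that may depend on tolerance, motivation or early response. Half of the experimental course is a different treatment from the control course, so the subjects who finish may be a different selection in each arm. A replacement adds a completer but does not recover the score of the person replaced. Nor is this only a choice of analysis set to be settled later, because a score that was never collected cannot be restored by any analysis.

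**Working it through.** **1. The plan's own figures.** The Power Analysis gives an ARAT effect size of 0.84, a one-tailed unpaired t-test, power above 0.80, 19 per arm, dropout 0.167 and 23 per arm recruited. The exact noncentral t calculation at one-sided alpha 0.05 gives power 0.795 with 18 per arm and 0.815 with 19, so 19 reproduces. For dropout, 19 / (1 − 0.167) = 22.8, which rounds up to 23 per arm, or 46. The sample size is not in question.

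**2. How many subjects could lack the endpoint.** 46 × 0.167 = 7.7, about 8, which also equals 46 − 38. This is a ceiling: the plan does not say when dropouts left the earlier study, and anyone who leaves after the 24-hour visit already has a post-treatment score.

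**3. Reading the provisions together.** The 24-hour evaluation follows 24 hours of treatment. A subject who stops at 20 hours does not meet that condition. No other provision schedules a test for that subject, and the Recruitment text replaces dropouts. No sentence says that early stoppers are not tested. That follows from the visit definition, the replacement rule and the absence of any other provision.

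**4. Timing between arms.** At three sessions a week, 12 / 3 = week 4 and 24 / 3 = week 8 in both arms. If each scheduled session is attended with probability p (an assumption, since the documents give no attendance data), the mean time to 24 sessions is 24 / (3p) = 8/p weeks:

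| p | Mean week of the 24-hour visit |
|---|---|
| 0.9 | 8.9 |
| 0.8 | 10.0 |
| 0.67 | 11.9 |
| 0.5 | 16.0 |

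One p applied to everyone shows spread among subjects and implies no difference between arms. A difference needs unequal attendance. For example, two sessions a week in one arm only would put that arm's visit at 24 / 2 = week 12 against week 8. The documents give nothing with which to choose such a value.

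**5. Cost in power of including early stoppers.** Assume that all 23 per arm are tested, that 16.7% stop early, that the SD is unchanged, and that stoppers contribute a fraction k of the full between-group effect. The diluted effect is 0.84 × [1 − 0.167 × (1 − k)].

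| Comparison | n per arm | Effect size | Power |
|---|---|---|---|
| Completers only, as planned | 19 | 0.84 | 0.815 |
| All tested, k = 1 | 23 | 0.84 | 0.877 |
| All tested, k = 0.5 | 23 | 0.770 | 0.823 |
| All tested, k = 0 | 23 | 0.700 | 0.755 |

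The extra scores offset the dilution when stoppers keep about half of the effect, and fall short when they keep none.

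**The case against.** The strongest reply is that dose and schedule are equal by design: one-hour sessions three times a week, no planned gap between blocks, and a control schedule stated to run in parallel. This stands. A reader might infer from the hours-based visits that the arms will be measured at different weeks or at different weekly doses. The documents do not support that. Any divergence would come from missed or delayed sessions, and its direction is open. The robot and its operator could delay the experimental arm's first block. But one therapist delivers all conventional therapy, and control subjects need that therapist for 24 sessions against 12, so therapist absence could delay controls more. Nor do the documents say that missed sessions are made up without limit. Outside PT and OT is logged and is a potential covariate.

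A second reply is that evaluating at fixed hours serves the hypotheses: Hypothesis I concerns the first 12 hours, and the power inputs are gains after a full course. This also stands. Moving every subject to a calendar trigger would trade equal dose for equal time, and the documents give no reason to prefer that trade.

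A third reply is that people who leave the study may refuse testing anyway, and that replacement protects power. Both are partly true. Some will decline, but stopping treatment is not the same as refusing evaluation, and the plan makes no distinction between them. Replacement protects the number of completers, not the comparison between randomised groups.

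**Conclusion.** The concern holds for subjects who stop treatment early. As written, the plan provides post-treatment scores only for those who complete the hours, so Hypothesis III becomes a comparison of completers. Up to about 8 of 46 subjects could be affected at 16.7% dropout. A reader might take that as a forecast of lost endpoints, but it is an upper figure. The size and direction of any bias cannot be calculated, because the plan gives neither the timing of dropout nor its reasons by arm.

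The conclusion rests on the plan's silence combined with its replacement rule, and a provision in the sections not available would change it. It does not extend to a claim that the arms differ in visit timing: nominal visits fall at weeks 4 and 8 in both. The stated sample size is unaffected.

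**What to change.** Leave the treatment rules, and the hours-based visits of subjects who complete, as they are. In the Overview and Clinical evaluations subsections of Section 5, add that:

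- every randomised subject who has not withdrawn consent is evaluated at each timepoint, whatever hours were received;
- subjects who stop treatment early are tested at the nominal times implied by the plan's own schedule, weeks 4 and 8, and at 6 months from a stated anchor common to both arms. The sponsor should set the visit window, including for someone who stops after a nominal week has passed.

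In Data analysis, state that these scores enter the Hypothesis III comparison in the group to which the subject was randomised, and that a replaced subject stays in it. Report hours received and elapsed weeks by arm, so that any difference in attendance can be seen.

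The cost is protocol wording and scheduling, with no evaluations beyond those planned for each subject. Including subjects with a partial course may dilute the full-dose effect somewhat, as the power table shows, and some who leave will decline testing, so missing scores will be reduced but not eliminated.
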